Erythroid response is defined in those who with a pretreatment hemoglobin of < 9.0 g/dL as an increase in hemoglobin concentration of ≥ 1.5 g/dL above baseline without transfusion, or reduction in the transfusion unit by at least 4 units for 8 consecutive weeks compared with the pretreatment transfusion requirement in the previous 8 weeks prior to the first administration of AMG531 (Day -55 to Day 1).

Neutrophil Response

Neutrophil response is defined in those with a pretreatment absolute neutrophil count (ANC) of $< 0.5 \times 10^9/L$ as a 100% increase over the baseline, or an increase in ANC of $> 0.5 \times 10^9/L$ in subjects with a pretreatment ANC of $< 1.0 \times 10^9/L$.

Baseline

Baseline values are defined as the values obtained before dosing AMG531 on Study Day 1. Data obtained during the screening period will serve as baseline values for those not measured or reported on Study Day 1. If multiple evaluations are performed during the screening period for a particular test, with the exception of platelet count, the values measured closest to the first administration of AMG531 will be considered as the baseline values (if hemoglobin concentration at Study Day 1 is within 28 days after RBC transfusion, hemoglobin concentration determined during the screening period will be used as baseline hemoglobin).

Baseline Platelet Count

Baseline platelet count is defined as the mean of two lowest platelet counts measured in 8 weeks prior to enrollment. Platelet count that is obtained within 7 days after platelet transfusion will not be used. The baseline platelet according to the definition of protocol Master Ver1.1 (The mean of two lowest platelet counts measured in 8 weeks prior to enrollment. Platelet count that is obtained within 3 days after platelet transfusion will not be used.) will be also collected .

Platelet Transfusion

Platelet transfusion given due to platelet count of $< 10 \times 10^9/L$ (prophylactic transfusion) or due to bleeding (therapeutic transfusion).

RBC Transfusion

RBC transfusion given due to the hemoglobin concentration of ≤ 9.0 g/dL or due to symptomatic anemia

Adverse Drug Reaction

Adverse events of which causal relationship to the investigational product cannot be ruled out (any events assessed to be other than “unlikely” or “not related”).

Study Duration

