3.3.1.2 Secondary endpoints

- The proportion of subjects achieving a platelet response any time during the initial dose evaluation period, Week1 through Week 12, Week 1 through Week 16, Week 1 through Week 24, and Week 1 through Week 52.
- The proportion of subjects who become platelet transfusion independent during the initial dose evaluation period, Week1 through Week 12, Week 1 through Week 16, Week 1 through Week 24, Week 1 through Week 52, Week 1 through Week 104, and Week1 through Week 156
- The proportion of subjects achieving erythroid response and/or neutrophil response during the initial dose evaluation period, Week1 through Week 12, Week 1 through Week 16, Week 1 through Week 24, Week 1 through Week 52, Week 1 through Week 104, and Week1 through Week 156
- Duration of platelet response
- Time to platelet response
- Changes in platelet count, hemoglobin concentration, and neutrophil count as continuous variables
- Changes in bone marrow cellularity and reticulin grade
- Changes in GIMEMA bleeding scale
- The proportion of subjects achieving tri-lineage responses
- The proportion of subjects able to discontinue study drugs after achieving normal level for 8 consecutive weeks without transfusion.
- Duration of study drug discontinuation while maintaining stable response

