3.4 Randomization

Subjects assessed to be eligible for the study will be randomized to either of the four dose groups (1, 3, 6, or 10 $\mu\text{g}/\text{kg}$) according to a static allocation procedure using the baseline platelet count (platelet $\leq 10 \times 10^9/\text{L}$ or $10 \times 10^9/\text{L} < \text{platelet} \leq 30 \times 10^9/\text{L}$). A written procedure for randomization will be created and the details will be specified in it.

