3.5 Target sample size

3.5.1 Efficacy and Safety

Eight in each cohort, a total of 32 subjects receiving AMG531 at a doses of 1, 3, 6 or 10 $\mu\text{g}/\text{kg}$ during the initial dose evaluation period will be assessed for the primary endpoint.

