6.2.3 Recording concomitant medication and therapy in electronic Case Report Form (eCRF)

All concomitant medication and therapy that a subject received during the period after enrollment through to the end of the study will be recorded on electronic case report form (eCRF) by the investigator with the following information for each concomitant medication and therapy: name of drug, route of administration, duration of treatment and justification for the administration. Agents not intended for medical treatment such as rehydration including saline solution, dissolving solution, or contrast medium for imaging diagnostics are not required to be recorded.

Platelet transfusions given between the period within 56 days (Day -55) prior to the first administration of AMG531 (Day 1) and RBC transfusion given between the period of within 26 weeks (Day -181) prior to the first administration of AMG531 (Day 1) through to the end of study will be recorded in eCRF, including date of each transfusion, volume of transfusion (unit and mL), platelet count or hemoglobin concentration before each transfusion, and reason for each transfusion.

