12.1.1.2 Secondary endpoint

The secondary endpoint will be evaluated based on the PPS. The proportion of subjects with a platelet response in any time during the initial dose evaluation period, Week 1 through Week 12, Week 1 through Week 16, Week 1 through Week 24, and Week 1 through Week 52 or the proportion of subjects achieving platelet transfusion independency during the initial dose evaluation period, Week 1 through Week 12, Week 1 through Week 16, Week 1 through Week 24, Week 1 through Week 52, Week 1 through Week 104, and Week 1 through Week 156 will be calculated in the same manner as the primary variables. Platelet transfusion independence is defined as achieving transfusion free period of at least 8 consecutive weeks.

The proportion of subjects with erythroid and/or neutrophil response during the initial dose evaluation period as well as in Week 1 through Week 12, Week 1 through Week 16, Week 1 through Week 24, Week 1 through Week 52, Week 1 through Week 104, and in

Week1 through Week 156 will be calculated in the same manner as the primary variables. An erythroid response is defined as achieving an increase in hemoglobin concentration of ≥ 1.5 g/dL above baseline without transfusion or reduction in the transfusion unit by at least 4 units for 8 consecutive weeks compared with the pretreatment transfusion requirement in the previous 8 weeks prior to the first administration of AMG531 (Day -55 to Day 1). A neutrophil response is defined in those with ANC of $< 0.5 \times 10^9/L$ as a 100% increase over the baseline, or an increase in ANC of $> 0.5 \times 10^9/L$ in subjects with a pretreatment ANC of $< 1.0 \times 10^9/L$.

Time to platelet response and duration of platelet response will be summarized.

The change in platelet counts, hemoglobin concentrations, and neutrophil counts from baseline will be summarized at each scheduled visit. For the transfusion, only the platelet transfusion given due to platelet count of $< 10 \times 10^9/L$ (prophylactic transfusion) or due to bleeding (therapeutic transfusion) and RBC transfusions of which hemoglobin concentration is ≤ 9.0 g/dL or due to symptomatic anemia will be included in the response assessment.

The changes in bone marrow cellularity and reticulin grade will be summarized by each subject based on the test reports. The changes in the GIMEMA bleeding scale will be summarized.

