12.2 Level of significance

Level of significance is not specified, since no statistical assumptions are provided in this study.

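### Erythroid and neutrophil response can be met by ordinary fluctuation in the longer reporting periods: one short baseline, many later chances, no confirmation and no untreated arm

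*Combined protocol and SAP*

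**What the plan says.** **Erythroid response** (Definition of Terms; 12.1.1.2) has two routes. One is a hemoglobin rise of at least 1.5 g/dL over baseline without transfusion. The other is a "reduction in the transfusion unit by at least 4 units for 8 consecutive weeks compared with the pretreatment transfusion requirement", the requirement being that observed "in the previous 8 weeks prior to the first administration of AMG531 (Day -55 to Day 1"). The Definition of Terms limits it to subjects with pretreatment hemoglobin below 9.0 g/dL.

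**Neutrophil response** is defined, for a pretreatment count below 0.5 x10^9/L, "as a 100% increase over the baseline". For a count below 1.0 it is a rise of more than 0.5. Baseline for hemoglobin and neutrophils is normally the one Day 1 value before dosing. Neither rule asks for a second value or a minimum duration.

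**Endpoint** (3.3.1.2): "The proportion of subjects achieving erythroid response and/or neutrophil response during the initial dose evaluation period", then over periods from Week 1 to Weeks 12, 16, 24, 52, 104 and 156. Hematology is weekly through Week 52 (8.2.2, 8.2.3). After that it is weekly, or two-weekly off drug (8.2.4).

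**Comparison.** Subjects "will be randomized to either of the four dose groups (1, 3, 6, or 10" µg/kg), so there is no untreated arm. Section 3.5.1 plans "Eight in each cohort, a total of 32 subjects receiving AMG531". Section 12.2 states: "Level of significance is not specified, since no statistical assumptions are provided in this study".

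**Longer transfusion record.** Section 6.2.3 collects "RBC transfusion given between the period of within 26 weeks (Day -181) prior to the first administration", and 8.2.1 lists it as a baseline characteristic. The response definitions use only the last 8 weeks.

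**The concern.** A single low baseline value, or one heavy 8-week transfusion run, tends to be followed by more ordinary values. The rule then accepts any qualifying visit or 8-week stretch in a period that keeps lengthening, so the chance of a false response can only grow with follow-up. With no untreated arm, the trial never observes the response rate of unchanged subjects and cannot subtract it.

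These proportions would support any statement that the drug acts beyond platelets. With 8 subjects per arm, one chance responder moves an arm's proportion by 1/8 = 12.5 points.

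**Working it through.** The plan states no power, expected rate or variability, so there is no planned figure to reproduce. The quantity worked out is the chance that a subject with no true change is scored a responder.

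**Inputs from the documents.** The response rules and baselines are as described above. Post-baseline weekly counts number 7 by Week 8, 23 by Week 24 and 51 by Week 52. Weeks 1-8 hold one 8-week transfusion window. Weeks 1-52 hold 52 - 8 + 1 = 45 windows stepped weekly.

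**Assumptions, not in the documents.**
- Neutrophils: constant true level 0.3 x10^9/L, lognormal, within-subject CV 20-40%, weekly correlation 0-0.5.
- Transfusion: constant need of 4-8 units per 8 weeks, 2 units per episode, interval CV 20-50%.
- 'During' a period is read as at any point in it. The plan says so expressly only for platelet response.

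**Step 1: one neutrophil count against one baseline.** Take σ = √ln(1 + CV²), two uncorrelated counts, and ignore the baseline cut-off. Then P(doubling) = 1 - Φ(ln 2 / (σ√2)).
- CV 20%: σ = 0.198, z = 2.48, P = 0.7%
- CV 30%: σ = 0.294, z = 1.67, P = 4.7%
- CV 40%: σ = 0.385, z = 1.27, P = 10%

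A single look is a modest problem. Repetition enlarges it.

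**Step 2: all looks, by simulation under the assumptions.**

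| Rule | Weeks 1-8 | By Week 24 | By Week 52 |
|---|---|---|---|
| Neutrophil, any visit (as planned) | 2-35% | 7-54% | 12-66% |
| Neutrophil, two consecutive visits | 0-12% | not shown | 1-39% |
| Transfusion, any 8-week window (as planned) | 4-17% | not shown | 11-61% |
| Transfusion, 8-week baseline against last 8 weeks | same single window | not shown | 1-16% |

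For transfusions in Weeks 1-8 there is only one window, so the error there is baseline noise. By Week 52, fixing the window while keeping the same baseline takes 11-61% down to about 1-16%. Choosing the best window is therefore the main cause in long periods.

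**Step 3: sensitivity to the transfusion assumptions.** If episodes are fully irregular (Poisson), the exact one-window chance with 2-unit episodes is 21.8%, 26.5% and 29.4% for means of 4, 6 and 8 units. If episodes are single units at interval CV 20-30%, the Week 52 chance is only 0-12% (mean need 4-12 units).

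**Step 4: hemoglobin route.** This assumes a true level of 8.0-8.5 g/dL and weekly correlation 0-0.8. With within-subject SD 0.3 the chance is about 0-1% by Week 52. With SD 0.5 it is 2-10% by Week 8 and 17-29% by Week 52. The 28-day exclusion after transfusion is not modelled and would remove looks.

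**Step 5: combining lineages.** Using the neutrophil and transfusion routes only, and assuming independence, the either-or chance is a + b - ab.
- Weeks 1-8: 0.02 + 0.04 - 0.001 = 6% up to 0.35 + 0.17 - 0.060 = 46%.
- By Week 52: 0.12 + 0.11 - 0.013 = 22% up to 0.66 + 0.61 - 0.403 = 87%.

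The rates accumulate but do not add: 66% + 61% would exceed 100%. Tri-lineage response needs all three lineages, so it cannot exceed the smallest of the three rates and is less affected.

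**Step 6: would the 26-week record be a better baseline?** With constant need it looks so: compared with the last 8 weeks, false response is at most 5%. With any window by Week 52 it is still 0-49%. Constant need is doubtful, however. Exclusion criterion 12 (5.3) bars ATG only within 6 months, and cyclosporine or anabolic hormone only within 6 weeks, before treatment. Suppose need fell from 8 to 4 units per 8 weeks just before the last 8 weeks. The 26-week baseline against the last window then gives roughly 13-35% false response, and the existing 8-week baseline roughly 1-14%, depending on how the change is modelled.

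**The case against.** **Variability is assumed.** This stands. At the low end the Week 1-8 chance is only 2-4%, so a reader who infers that unchanged subjects easily become responders within 8 weeks goes further than the material allows.

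**Not every unchanged subject gets 51 looks.** This stands in part. Under 6.1.2 and 6.1.2.1, platelet non-responders may step up a dose level every 4 weeks, and 11.1.1 item 4 withdraws those without response after 8 weeks at the top level. From the 10 µg/kg group that takes three steps (Weeks 9, 13, 17) plus 8 weeks, so Week 25 at the earliest. From the 1 µg/kg group it takes six steps, so Week 37. Later steps are discretionary. With 23 counts the neutrophil chance is still 7-54%. Beyond Week 52 only platelet responders continue (5.4).

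**The plan has safeguards.** It excludes hemoglobin within 28 days of transfusion and neutrophils within 7 days of rescue G-CSF, uses scheduled visits only, and limits which transfusions count. These deal with contamination by rescue, not with regression to the mean or repeated looks. The FAS analysis repeats the same rule.

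**Other outputs would expose fluctuation.** Change is summarized at every visit, and normal levels held for 8 consecutive weeks are reported. Chance response should also not rise with randomized dose. These help interpretation, but they do not correct the response proportions. The dose contrast is clean only up to Week 8 and rests on 8 per arm.

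**The unused 26-week record.** A reader might infer that ignoring it is the defect and that claims should rest on it. The documents do not support that: the permitted recent therapy means it may not describe need off treatment. The 8-week window lies mostly (42 of 56 days) inside the 6-week cyclosporine exclusion. The detailed SAP announced in 12.5 is also not available, so non-use can be stated only for these documents.

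**Conclusion.** The point holds for the secondary erythroid and neutrophil endpoints, most clearly in the longer periods. For a subject with no true change, false response is about 2-35% (neutrophil) and 4-17% (transfusion rule) in Weeks 1-8. By Week 52 it is 12-66% and 11-61% for those who remain in the study. The ranges depend on the assumed variability and on reading 'during' as any time. The direction follows from the rule itself.

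A reader might go on to infer that a reported multilineage benefit would be no more than noise. The documents do not support that. They show only that the proportions as defined cannot separate effect from fluctuation, and they plan no formal test. Tri-lineage response is less exposed, and the primary endpoint, read at one visit, is untouched.

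**What to change.** Keep the published definitions. Before database lock, add to 12.1.1.2, as companion sensitivity analyses:

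1. Neutrophil response with the criterion met at two consecutive scheduled visits.
2. The 4-unit transfusion rule with the existing 8-week baseline, compared with the last 8 weeks of each reporting period. State a rule for subjects withdrawn before that window (for example, scored as non-responders), since 12.4 does not impute.

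State whether 'during' means at any time, and interpret any multilineage claim in the light of both analyses. The 26-week record may be shown as a further sensitivity analysis, with the prior-therapy caveat, but not as the basis of a claim.

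**Limits.** The first analysis reduces chance neutrophil response by Week 52 but does not remove it. The second changes nothing in Weeks 1-8 and measures end-of-period rather than ever-response. Neither covers the hemoglobin route, which should be read with the visit-by-visit changes.

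**Cost.** SAP wording and programming, no new data. Response proportions will look less favorable.

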Study duration of each subject in this study is specified as the period from the day of obtaining written informed consent through the end of examinations on completion of treatment (or withdrawal).

Observation and Examination Period

In this study, Week 1 (Day 1) is defined to be the day of initial administration of AMG531. Initial dose evaluation period is defined to be the period from Week 1 to Week 8, Extension period is the period from Week 9 to Week 52, and Long-term treatment period is the period from Week 53 to Week 156.

Aplastic Anemia with Refractory Thrombocytopenia

Aplastic anemia with thrombocytopenia defined as platelet count of $\leq 30 \times 10^9/L$ that does not respond to the immunosuppressive therapy (ATG + cyclosporine), or relapsed after having showed response.

Transfusion Independence

Achieving platelet or RBC transfusion free period of at least 8 consecutive weeks.

Tri-lineage response

Tri-lineage response is defined in those achieving platelet response, erythroid response, and neutrophil response all together.

Normal level

Normal level is defined as platelet counts $>50 \times 10^9/L$, hemoglobin concentration >10.0 g/dL, and neutrophil counts $>1.0 \times 10^9/L$

Stable response

Stable response is defined as platelet counts $\geq 30 \times 10^9/L$, hemoglobin concentration ≥ 9.0 g/dL, and neutrophil counts $\geq 0.5 \times 10^9/L$ maintained during dose tapering or discontinuation without transfusion

Cytogenetic abnormality

Any cytogenetic abnormalities newly emerged during or after the initiation of AMG531 treatment

PROTOCOL SYNOPSIS

I TITLE

A phase 2, Randomized, Open-Label, Parallel, Comparative, Dose-Finding Study to Evaluate the Efficacy and Safety of AMG531 in Aplastic Anemia (AA) Subjects with Thrombocytopenia Refractory to Immunosuppressive Therapy

[figure not shown]
II STUDY OBJECTIVES

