11 STOPPING RULES AND PROCEDURES

11.1 Subject withdrawal

11.1.1 Criteria for subject withdrawal

Any of the following circumstances will result in the subject being withdrawn from the study:

- 1) The subject is found to be ineligible for participation in this study due to violations in the inclusion or exclusion criteria specified in the study protocol;
- 2) The subject decides to discontinue his/her participation in the study;
- 3) The subject becomes unable to undergo necessary observations or examinations;
- 4) The subject who does not achieve a platelet response after 8-week treatment with AMG531 20 µg/kg QW;
- 5) The investigator considers that the subject should be withdrawn from the study due to an adverse event (including progression of the primary disease);
- 6) The subject received any of the prohibited concomitant medications or treatments;
- 7) The subject becomes pregnant or wants to have children during the study;
- 8) The investigator assesses that the subject needs to be withdrawn from the study for any reason not specified above.
- 9) The subject who does not meet the entry criteria for long-term treatment period

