12 STATISTICAL ANALYSIS

12.1 Statistical methods

Generally, categorical variables will be summarized by the number of subjects and the percentage of subjects in each category to the total number of subjects, and continuous variables will be summarized by descriptive statistics (number of subjects, mean, standard deviation, median, minimum, and maximum). Coefficient of variation and geometric mean will be also presented to summarize pharmacokinetic parameters.

Data will be cut off, collected and analyzed when all subjects complete the observations at week 17.

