Tri-lineage response is defined in those achieving platelet response, erythroid response, and neutrophil response all together. The proportion of subjects with tri-lineage response will be calculated in the same manner as the primary variables. Time to tri-lineage response will be summarized.

The proportion of subjects who achieved normal level for 8 consecutive weeks, who started tapering, and who discontinued study drug will be calculated. Time to achieving normal level for 8 consecutive weeks (the initial day of the period), to starting tapering, to discontinuing study drug as a result of tapering will be summarized.

Longest duration of drug discontinuation in subjects while maintaining stable response will be summarized.

Robustness of the results will be evaluated by the analysis calculated in the same manner based on the FAS.

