12.4 Handling of missing, unused, and abnormal data

Any missing data on platelet, hemoglobin, and neutrophil for evaluating efficacy response will be handled as a missing value and will not be imputed with an alternative value using a statistical approach.

If data from a particular subject needs to be examined how to handle them because of an event unexpected at the start of the study, how to treat such data will be decided before database lock.

12.5 Development of the statistical analysis plan and procedure for reporting deviations from the original statistical analysis plan

The detailed statistical analysis plan including the analyses described in this section will be finalized before database lock. Any major change to the statistical analysis plan will be described in the clinical study report.

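### Times to and durations of response fall to a default mean/median summary with no censoring rule, leaving ongoing responses, ongoing off-drug periods and non-responders without a defined place

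*Combined protocol and SAP*

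**What the plan says.** Section 12.1.1.2 (Secondary endpoint) gives the analysis of these endpoints in single sentences:

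- "Time to platelet response and duration of platelet response will be summarized".
- "Time to tri-lineage response will be summarized".
- "Longest duration of drug discontinuation in subjects while maintaining stable response will be summarized".
- Times to normal level, to the start of tapering and to discontinuation through tapering are treated in the same way.

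No statistic is named. Section 12.1 (Statistical methods) supplies the default: "continuous variables will be summarized by descriptive statistics (number of subjects, mean, standard deviation, median, minimum, and maximum". That sentence is introduced as a general rule. Section 12.4 covers missing blood counts only: a missing value "will be handled as a missing value and will not be imputed with an alternative value using a statistical approach".

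Several features of the design make incomplete observations certain or likely:

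- Section 12.1: "Data will be cut off, collected and analyzed when all subjects complete the observations at week 17".
- Definition of Terms: "Long-term treatment period is the period from Week 53 to Week 156", so treatment follow-up has a fixed end.
- Section 11.1.1 withdraws, among others, this group: "The subject who does not achieve a platelet response after 8-week treatment with AMG531 20 µg/kg QW". It also withdraws subjects who do not qualify for the long-term period.
- Under section 6.1.3.3, a subject who keeps a stable response off drug is not re-dosed, so the off-drug period can run to the end of observation.

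Section 12.5 leaves a detailed SAP to be finalized before database lock. The documents contain no separate text from it on this point.

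**The concern.** A duration still running when data are cut is known only to exceed the time observed. Mean, SD and median have no way to carry that information. The analyst must either enter the observed length as if the response had ended, or leave the subject out. Both shorten the reported duration, and the shortening grows with the share of responses still ongoing. Off-drug periods have the same problem, and there the most successful subjects are the ones cut short.

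Time to response has the mirror problem. A subject who never responds has no value to enter, so a plain summary describes responders only. An arm with few but early responders then looks faster than an arm where most subjects respond over a longer time.

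At stake is how the secondary results are read across four arms of eight. In a descriptive study these figures are presented as they stand, with no model behind them.

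**Working it through.** The plan gives no figure for these endpoints, so there is nothing to reproduce. The calculations below illustrate size. Their distributional inputs are assumptions and are not taken from the documents.

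**Duration of response**

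Assumptions: exponential duration with true median M, and response onset at Week 5. From the documents: a Week 17 cut, an extension period ending at Week 52, and long-term treatment ending at Week 156. Follow-up c after onset is therefore 17 − 5 = 12, 52 − 5 = 47, or 156 − 5 = 151 weeks.

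Formulas, with λ = ln 2 / M:

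- true mean = 1/λ
- share still ongoing = exp(−λc)
- plain mean with ongoing responses entered as finished = (1 − exp(−λc))/λ
- plain median = the smaller of M and c
- median of ended responses only = −ln(1 − p/2)/λ, with p = 1 − exp(−λc)

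For M = 24 and c = 12: λ = 0.6931/24 = 0.02888; exp(−0.3466) = 0.707, so 71% are ongoing; plain mean = 0.293/0.02888 = 10.1 weeks; true mean = 1/0.02888 = 34.6 weeks; plain median = 12 weeks. With ended responses only, p = 0.293 and the median is −ln(0.8536)/0.02888 = 5.5 weeks.

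| c (weeks) | M (weeks) | Ongoing | Plain mean | True mean |
|---|---|---|---|---|
| 12 | 12 | 50% | 8.7 | 17.3 |
| 12 | 24 | 71% | 10.1 | 34.6 |
| 12 | 48 | 84% | 11.0 | 69.2 |
| 47 | 24 | 26% | 25.7 | 34.6 |
| 151 | 24 | 1% | 34.2 | 34.6 |
| 151 | 48 | 11% | 61.4 | 69.2 |

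At c = 12, a fourfold range in true means (17.3 to 69.2) shrinks to about 1.3-fold (8.7 to 11.0).

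Sensitivity to the assumptions: with onset at Week 9 (8 weeks to the Week 17 cut) and true medians of 26 to 208 weeks, 81% to 97% are ongoing, the plain mean is 7.2 to 7.9 weeks, and the plain median is 8 weeks whatever the truth. Followed to Week 157, a true median of 52 gives a plain mean of 64.6 against 75 weeks, 104 gives 94 against 150, and 208 gives 117 against 300. The late bias is therefore modest for medians up to about a year and grows if responses last longer.

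**Time to response**

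Simple case: in an arm of 8, two subjects respond, at Weeks 4 and 6, and nobody leaves earlier. The responders-only median is 5 weeks. Kaplan-Meier gives 1 − 2/8 = 75% still without response, so the median is not reached.

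General case, assuming exponential time to response with a proportion p responding by Week 52: λ = −ln(1 − p)/52, all-subject median = ln 2/λ, responders-only median = −ln(1 − p/2)/λ.

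| p | Responders-only median | All-subject median |
|---|---|---|
| 30% | 23.7 | not reached by Week 52 |
| 50% | 21.6 | 52.0 |
| 70% | 18.6 | 29.9 |
| 85% | 15.2 | 19.0 |

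The responders-only figure moves by 8.5 weeks (23.7 − 15.2) while the response rate nearly triples.

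**The case against.** Four arguments against the point have force.

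- **The default is inferred.** Section 12.1 states a general rule, and section 12.1.1.2 names no statistic for these endpoints. Elsewhere (12.1.2, and 12.1.3 for laboratory tests and vital signs) the plan calls for descriptive statistics explicitly. Section 12.5 leaves detail to a later SAP, where censoring rules usually sit. A reader might infer that the sponsor has decided to treat ongoing responses as finished and to discard non-responders. The documents do not say so. It is what follows if the only available rule is applied.
- **The Week 17 figures are the severe case.** If the cut is a calendar date, Week 17 is the last subject's position and earlier enrollees have longer follow-up. At the assumed onset, 12 weeks is then the minimum, so 71% ongoing overstates the whole-study share.
- **The link to dose choice is weak.** A reader might infer that the recommended dose would be biased. The primary measure for comparing the four initial doses is response at Week 9 (3.3.1.1, 12.1.1.1), and no section makes time to or duration of response a selection criterion. From Week 9 doses may be raised or adjusted (6.1.2), so later results by randomized arm mix doses whatever the estimator.
- **Response proportions appear alongside.** In the 2/8 example a reader would also see 25% response.

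All four limit the claim. None supplies the missing rule: if the verb is read as unspecified instead of as the default, there is still no method and no censoring.

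**Conclusion.** The gap is real and worth closing. As the text stands, the listed times and durations have only a mean/median default, and incomplete observations are built into the design. Under exponential durations with a true median of 24 weeks and onset at Week 5, the plain mean at minimum Week 17 follow-up is about 10 weeks against 34.6. By Week 156 the shortfall is small to moderate for true medians of 24 to 48 weeks, and larger if responses last much longer. Responders-only time to response barely reflects how many subjects respond.

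The consequence is limited to descriptive secondary endpoints. Section 12.2 sets no significance level, and the primary endpoint is unaffected. Duration by randomized dose should be read as describing a starting-dose strategy. The documents do not support saying that a biased analysis has been chosen or that the dose recommendation is compromised.

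**What to change.** In section 12.1.1.2, or in the SAP before database lock:

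- Define when a platelet response starts and ends. Without this, no duration can be computed by any method.
- Report time to platelet response and duration of response by Kaplan-Meier, by randomized dose. Censor non-responders and ongoing responses at the last evaluable scheduled count before cut-off or withdrawal. State how death and transplantation are treated.
- Do the same for off-drug duration, censoring periods still ongoing.
- Restrict time to tri-lineage response to subjects whose baseline values make them evaluable. The Definition of Terms ties erythroid and neutrophil response to baseline hemoglobin and neutrophil thresholds, so some subjects cannot have the event.
- For normal level, tapering and discontinuation, give cumulative proportions with all subjects in the denominator. Treat withdrawal or failure to enter the long-term period as a competing event. Tapering exists only in that period, so simple censoring would treat those subjects as still able to taper and would overstate the proportions.
- Show the number ongoing or censored, and label any responders-only table as such.

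The cost is a few lines of text, with no change to conduct or data collection. With about 8 subjects per arm, some medians will be not reached and the estimates will be imprecise.
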